6.2.3.3 Other HRQoL and PRO associated endpoints

- Descriptive assessment will be done on the basis of the VAS and on dimension level assessment basis.

Frequency tables providing the number and percentages of the different response options to individual questions will be displayed. In addition, changes from baseline for the single questions will be displayed with shift tables by treatment.

The EQ visual analogue scale (VAS) values of the EQ-5D-5L and their changes to ue baseline will be summarized by treatment as continuous variable; arithmetic mean, SD, minimum, quartiles, median and maximum will be displayed by treatment.

The scoring algorithm described in the EQ-5D-5L manual will be used.

- EIS single items, EIS physical subscale, EIS emotional subscale, and the eight remaining EIS individual items during baseline, at weeks 4/8/end of

intervention/FUP1/FUP2 and absolute change from each week after start of intervention to baseline. Full details of scoring algorithms and transformation of domain scores and single item scores are provided in Section 8 Appendix 1.

- VAS for pelvic pain at baseline, at weeks 4/8/end of intervention/FUP1/FUP2 and absolute change from each visit after start of intervention to baseline
- Patient Global Impression of Change (PGI-C) and change from baseline in Patient Global Impression of Severity (PGI-S), at visit 3, 4 and 5. Frequency tables providing the number and percentages of the different response options to individual questions will be displayed for PGI-S and PGI-C. In addition, changes from baseline for PGI-S and changes from Visit 3 for PGI-C will be displayed using shift tables for the single questions.
- PAQ (Productivity Activity Questionnaire). single items at screening and end of intervention; absolute change of PAQ individual items from end of intervention to screening
- PainDETECT single items and total score at baseline, end of intervention/FUP1/FUP2 and absolute change from end of intervention/end of follow-up to baseline for numeric items and shift tables for categorical items.
- PCS single items, subscales, and total score at baseline
- Absolute change in PSQ3 single items from end of intervention to baseline

These summary statistics and difference to baseline will be presented by treatment.

6.3 Pharmacokinetics/pharmacodynamics (PK/ PD)

BAY 1817080 plasma concentrations will be summarized by intervention group, visit, and planned sampling time. Box-plots showing plasma concentration vs timepoint will be created for each intervention, highlighting patients who fulfill the criteria for close liver observation.

6.4 Safety

All variables in this section will be analyzed descriptively based on the SAF.

6.4.1 Adverse events (AEs)

All AEs will be collected from signing the informed consent until the SFU visit.

A treatment-emergent AE (TEAE) is defined as any event arising or worsening after the start of study drug administration until 14 days after the last study medication intake.

The incidence of TEAEs will be assessed as secondary safety endpoint. The incidence of AEs and TEAEs will be analyzed by descriptive statistics, such as frequency tables.

An overall summary of the number and percentage of participants with AEs and TEAE will be presented. In addition, all AEs and TEAEs will be tabulated according to the affected system organ class and preferred term, as coded by the Medical Dictionary for Regulatory Affairs (MedDRA).

The frequency of the AEs related to potential and identified risks of Eliapixant will be displayed. Regarding the identification specifications for these AEs, the following SMQs and PTs will be applied:

1. SMQ “Taste and smell disorders”

2. SMQ “Hemorrhages”
3. MLG Hypotension
 - PT: Blood pressure ambulatory decreased;
 - PT: Blood pressure decreased;
 - PT: Blood pressure diastolic decreased
 - PT: Blood pressure systolic decreased;
 - PT: Diastolic hypotension
 - PT: Hypotension;
 - PT: Mean arterial pressure decreased
 - PT: Heart rate decreased
 - PT: Bradyarrhythmia
 - PT: Bradycardia
 - PT: Sinus bradycardia
 - PT: Dizziness
 - PT: Dizziness postural
 - PT: Dizziness exertional
 - PT: Syncope
 - PT: Presyncope
 - PT: Loss of consciousness
 - PT: Blood pressure orthostatic decreased;
 - PT: Orthostatic hypotension;
4. SMQ “Drug related hepatic disorders - comprehensive search”

Further tables will be provided for serious and/or drug related TEAEs. Tables for non-serious TEAEs will also be provided.

In addition, a separate table summarizing TEAEs that occurred in more than 5% of the subjects will be provided.

The incidence of all AEs during pre-treatment and during post-treatment (that is, AEs occurring more than 14 days after end of treatment with study drug) will be tabulated separately.

The summaries will be tabulated by intervention group and overall.

Serious adverse events, deaths and adverse events leading to discontinuation will be listed. The date, relative day (to study intervention) and treatment-emergent flag will be included.

Further summaries of adverse events by intensity and worst outcome, may be provided, consistent with Bayer Global Medical Standards.

6.4.1.1 Taste-related and smell-related AEs

Impairment or loss of smell and/or taste is a common symptom of COVID-19. Taste-related/smell-related AEs as well as the responses to the questions of the taste/smell disturbance assessments will be analyzed using descriptive statistics.

To distinguish P2X3 related taste AEs from COVID-19 related smell/taste AEs the details of smell/taste disturbance assessments will be evaluated together with the SARS-CoV-2/serology IgG test results, the AEs confirming COVID-19 and the timing information by individual patient review.

SMQ “Taste and smell AEs” has 14 MedDRA PTs, these will be divided in two categories one for “Taste AEs” and one for “Smell-Related AEs” as follows:

The following preferred terms will be combined into the “Taste AE” - category:

PT: Ageusia

PT: Dysgeusia

PT: Gustometry abnormal

PT: Hallucination, gustatory

PT: Hypergeusia

PT: Hypogeusia

PT: Taste disorder

The following preferred terms will instead be included in the “Smell-related AEs” category:

PT: Anosmia

PT: Congenital anosmia

PT: Hallucination, olfactory

PT: Hyposmia

PT: Olfactory nerve disorder

PT: Olfactory test abnormal

PT: Parosmia

Taste- and smell-related AEs, along with responses about frequency and bothersomeness, will be analyzed using descriptive statistics.

In addition, the dose-dependency of taste-related AEs will be assessed using a logistic regression model with treatment as factor. The odds ratio and its 80% and 95% confidence intervals, and the p-value for treatment comparisons from the logistic regression model will be provided. Only taste-related AEs that cannot be attributed to a SARS-CoV-2 infection will be considered for the model.

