For example if a participant has the EQ5D questionnaire pushed on day 3 after starting her treatment period, the responses will be counted as baseline.

The above rule for the EQ5D will also apply to the follow-up cycles.

Bleeding episode

The sponsor's standard procedures defines a bleeding episode as "day(s) with bleeding/spotting of which at least one day is of intensity "light" or higher, preceded and followed by at least 2 bleed-free days" [2]. Bleeding episodes will be derived from the ESD.

An episode is left censored if it starts at or before day 2 of the diary. Left censored episodes are expected to count to the previous cycle / reference period and are therefore ignored in all

episode related evaluations. Bleeding / spotting days of left censored episodes are evaluated in all day related evaluations as they would for not left censored episodes.

Likewise, for bleeding/spotting on the second last or last study day, the unobservable following two bleed-free days will be assumed to be given.

The reason for this is that each bleeding/spotting episode, spotting only episode, or bleeding free interval is attributed to the reference period in which it begins.

In addition, if a participant does not experience any bleeding days during the 28-day cycle, the observations collected will not be assessed for the dysmenorrhea endpoint.

Numerical coding of ESD values when response is not expected by design

The ESD device is programmed such that items 2 (worst constant pain) and 3 (worst short-term pain) are not administered if the participant reports no pain for item 1 (pain at its worst). Based on the logical relation of the questions, the values for items 2 and 3 will be set to 0 when item 1 = 0.

COVID-19 infection

The start of an active COVID-19 infection is defined as the date of the first positive SARS-CoV-2 RNA test or the start date of the AE confirming the COVID-19 infection, whichever is earliest. For participants with documented vaccination against COVID-19 during the study, positive serology IgG tests post vaccination will not be considered an active COVID-19 infection.

For the relevant MedDRA preferred terms see Appendix 3 [3]

The distinguishment of P2X3 related taste AEs from COVID-19 related smell/taste symptoms will be done by individual patient review based on the details of smell/taste disturbance assessments, the SARS-CoV-2/serology IgG test results, the AEs confirming COVID-19 and the timing information.

Rescue Medication

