6.1 Population characteristics

All variables in this section will be analyzed descriptively. The analyses will be based on the FAS and pPPS, unless otherwise specified.

Any table displaying demographics and baseline characteristics will be repeated for the following COVID-19 pandemic related subgroups:

all randomized subjects affected by COVID-19 pandemic related study disruption
all randomized subjects with COVID-19 adverse event and/or positive SARS-CoV-2 PCR test
and/or positive serology IgG test after start of treatment

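### The COVID-19 subgroup counts IgG positivity without a negative baseline, and the taste-AE model excludes events after a review with no seroconversion rule, no stated blinding and no all-event counterpart

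*SAP*

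**What the plan says.** **COVID-19 subgroup.** SAP 6.1 states: "Any table displaying demographics and baseline characteristics will be repeated for the following COVID-19 pandemic related subgroups". One of the two subgroups is all randomised women with a COVID-19 AE, a positive PCR test, "and/or positive serology IgG test after start of treatment". The Visit 1a result plays no part.

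**Active infection.** SAP 4.5 uses a different rule. The start of an infection "is defined as the date of the first positive SARS-CoV-2 RNA test or the start date of the AE confirming the COVID-19 infection", whichever comes first. On serology it adds: "For participants with documented vaccination against COVID-19 during the study, positive serology IgG tests post vaccination will not be considered an active COVID-19 infection". It says nothing about vaccination or infection before the study.

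**Taste events.** SAP 4.5 says that separating drug-related from COVID-19-related taste events "will be done by individual patient review based on the details of smell/taste disturbance assessments", together with the SARS-CoV-2 and IgG results, the COVID-19 AEs and the timing. SAP 6.4.1.1 repeats these inputs, ending with "the AEs confirming COVID-19 and the timing information by individual patient review". The logistic model with treatment as factor is then restricted: "Only taste-related AEs that cannot be attributed to a SARS-CoV-2 infection will be considered for the model". It reports odds ratios with 80% and 95% intervals and p-values.

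**Serology schedule.** The protocol's Schedule of Activities and Table 10–1 place antibody tests at Visit 1a and at the last follow-up visit only (Visit 6 or 7).

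**The concern.** IgG shows past exposure or vaccination at an unknown date. Used without the baseline result, it cannot separate a woman infected on study from one who was already immune at entry. This matters in two separate places.

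In SAP 6.1 the rule is fixed, so the misclassification is certain for any woman who enters IgG-positive and remains so. The tables would then describe a mixture of on-study infections and earlier immunity.

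In SAP 6.4.1.1 the problem is discretion. Taste disturbance is the compound's identified risk (Protocol 2.3.1), and this model is the only planned inferential analysis of its dose-dependency. Events leave the model on a judgement that may use IgG. The SAP does not say how IgG is weighed, what time window applies, or whether the reviewer knows the arm. Because a retained event is one that cannot be attributed to infection, a literal reading also drops doubtful events. A genuine drug effect could be removed, and no all-event model would show how much the result depends on the review.

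**Working it through.** **1. Can women enter already IgG-positive?** Yes. Protocol 5.2 (criteria 15 to 17) excludes a positive RNA test or a contact within 4 weeks before Visit 1a, and persisting symptoms after COVID-19. Resolved infection and earlier vaccination are allowed. The exemption in SAP 4.5 covers vaccination during the study only, and SAP 6.1 does not refer to it.

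**2. Can the later IgG date an infection?** No. It is taken 38 or 90 days after the last dose (each ±3). The treatment-emergent window closes 14 days after the last dose (SAP 6.4.1). The sample therefore falls 38 − 14 = 24 or 90 − 14 = 76 days after that window, and an infection during follow-up could turn it positive. Under Protocol 4.1, elagolix women are followed for 38 days and the blinded arms for 90, so the time available to become positive differs between elagolix and the blinded arms, though not among the blinded arms.

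**3. Does the subgroup rule feed the taste model?** No. SAP 6.1 governs repeated demographic and baseline tables. The model depends on the individual review, in which IgG is one input among several.

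**4. Is the review blinded?** This is not stated. SAP 4.6 places monitoring of women who contracted COVID-19 in the blind review and points to 4.5, but does not name taste attribution. Elagolix is open-label.

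**5. What would wrong removal do?** The plan gives no figure to reproduce, so this is an illustration. Inputs from Protocol 2.3.1 (study 18184) are taste-AE rates of 20.5% at the dose corresponding to 150 mg BID and 2.5% on placebo. The planned group size is 420/5 = 84. The assumption, not in the documents, is that a share s of taste events is wrongly removed, equally in both arms.

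The rates become p(1 − s). The risk ratio stays at 20.5/2.5 = 8.2 for every s. The odds ratio is [p₁/(1 − p₁)]/[p₀/(1 − p₀)]. Power is for a two-sided 5% comparison of two proportions by the normal approximation, Φ[(|p₁ − p₀| − 1.96·se₀)/se₁], with se₀ pooled and se₁ unpooled.

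| s | Rates, 150 mg v placebo | Expected events | OR | Power |
|---|---|---|---|---|
| 0 | 20.5% v 2.5% | 17.2 v 2.1 | 10.1 | 96% |
| 0.1 | 18.5% v 2.3% | 15.5 v 1.9 | 9.8 | 94% |
| 0.3 | 14.4% v 1.8% | 12.1 v 1.5 | 9.4 | 86% |
| 0.5 | 10.3% v 1.3% | 8.6 v 1.1 | 9.0 | 71% |

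Equal removal costs events and power and barely moves the OR. Unequal removal is different. If 30% of events were removed at 150 mg and none on placebo, the OR would be (0.1435/0.8565)/(0.025/0.975) = 6.5; with the reverse pattern it would be (0.205/0.795)/(0.0175/0.9825) = 14.5.

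The study stopped early (SAP 4.4), so actual groups may be smaller than 84. The power column shows direction, not the power this trial will have.

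**The case against.** The case against is substantial.

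- **IgG is not the SAP's definition of active infection, and no rule removes a taste event on IgG alone.** This stands. The reviewer also has AE and timing data, and Visit 1a serology shows who was already positive. What is missing is any requirement to use that baseline result.
- **Better evidence is already collected.** Protocol 10.2 requires RNA testing when COVID-19 symptoms are reported, including new loss of taste or smell. This stands too, and it is why the fix is feasible. However, the trigger names loss, and the review is not told to prefer a dated RNA result to an undated IgG.
- **Nothing is hidden.** SAP 6.4.1 and 6.4.1.1 tabulate taste events with no stated COVID-19 exclusion. This limits the harm, but it does not show how the model's estimate depends on the attributions.
- **An all-event model has its own distortion.** COVID-19 taste loss that is balanced between arms pulls the OR towards 1. With an assumed independent background of 2%, the rates are 1 − 0.795×0.98 = 22.1% and 1 − 0.975×0.98 = 4.5%, giving an OR of about 6.1. With 5% they are 24.5% and 7.4%, giving about 4.1. This is a good reason not to make the all-event model the main one. It does not argue against running it as a sensitivity analysis.

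**Conclusion.** Two limited defects stand. First, the SAP 6.1 subgroup misclassifies women who were immune before entry. This follows directly from the text and affects descriptive tables only. Second, the only inferential analysis of an identified risk excludes events after a review that has no seroconversion condition, time window or stated blinding, and no all-event model stands beside it.

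The size is unknown. The documents give neither the share of women seropositive at entry nor the share of taste events that would be removed. The illustration depends on the assumed s and on rates from another population. If removal is equal across arms, the effect is mainly lost events and power; material bias in the OR needs removal that differs by arm. The documents leave that possible but do not plan it.

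A reader might infer that any positive IgG makes a woman a case and removes her taste events. With an assumed 30 to 70% seropositive at entry, the 18-point difference (20.5 − 2.5) would then shrink to 18 × 0.7 = 12.6 or 18 × 0.3 = 5.4 points. The documents do not support this. SAP 4.5 dates infection by RNA test or AE, the 6.1 subgroup does not feed the model, and the review weighs several inputs. The range would need every taste event in every seropositive woman to be discarded, which nothing in the plan prescribes.

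**What to change.** **SAP 4.5 and 6.1.** Count IgG as evidence of on-study infection only on seroconversion, meaning negative at Visit 1a and positive later, in a woman not vaccinated before or during the study. Visit 1a serology is already collected, so no new test is needed.

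**SAP 6.4.1.1.** State that attribution of taste events is completed at blind review, before unblinding, and name it in SAP 4.6. Require a positive RNA test or a COVID-19 AE close in time to the taste event, with the window fixed in advance, so that IgG alone removes no event. Add a sensitivity logistic model on all taste-related AEs beside the planned one.

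**Cost.** Some SAP wording and one extra model run. The all-event model carries some COVID-19 background that pulls its OR towards 1, so the two models should be read together.

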6.4.2 Study Treatment Duration and Exposure

Study treatment duration and the average daily dose will be summarized overall for SAF. The duration of study treatment (in days) is derived by the following formula:

last dose date – first dose date + 1- number of days treatment was interrupted due to COVID-19 pandemic-related reasons.

Descriptive statistics of treatment duration will be presented.

The number of tablets taken will be summarized descriptively by treatment group and overall.

Using the drug accountability data, the average daily dose for overall study is calculated for subjects on active treatment based on the following formulas depending on the treatment arm:

For the 25mg treatment arm

$$25\text{mg} \cdot \frac{\frac{1}{3} \cdot \text{Total Number of 25mg tablets taken}}{\text{min}(\text{last tablets returned date, last treatment intake date}) - \text{first tablets dispensed date}}$$

For the 75mg treatment arm

$$25\text{mg} \cdot \frac{\text{Total Number of 25mg tablets taken}}{\text{min}(\text{last tablets returned date, last treatment intake date}) - \text{first tablets dispensed date}}$$

For the 150mg treatment arm

$$25\text{mg} \cdot \frac{\frac{2}{3} \cdot \text{Total Number of 25mg tablets taken}}{\text{min}(\text{last tablets returned date, last treatment intake date}) - \text{first tablets dispensed date}}$$

$$+100\text{mg} \cdot \frac{\text{Total Number of 100mg tablets taken}}{\text{min}(\text{last tablets returned date, last treatment intake date}) - \text{first tablets dispensed date}}$$

For the Elagolix arm

$$150\text{m} \cdot \frac{\text{Total Number of 150mg Elagolix tablets taken}}{[\text{min}(\text{last tablets returned date, last treatment intake date}) - \text{first tablets dispensed date}) + 1]}$$

Overall Compliance will be calculated as

$$\frac{\text{Total Number of 25mg tablets taken} + 4 \cdot \text{Total Number of 100mg tablets taken}}{14 \cdot (\text{min}(\text{last tablets returned date, last treatment intake date}) - \text{first tablets dispensed date})}$$

In addition, overall Compliance for the Elagolix arm will be calculated as

$$\frac{\text{Total number of 150mg Elagolix tablets taken}}{[\text{min}(\text{last tablets returned date, last treatment intake date}) - \text{first tablets dispensed date}) + 1]}$$

Compliance between visits will be calculated as

$$\frac{\text{Number of 25mg tablets taken between visits} + 4 \cdot \text{Number of 100mg tablets taken between visits.}}{14 \cdot (\text{min}(\text{tablets returned date; last treatment intake}) \text{ at Visit } x - \text{tablets dispensed date at Visit } (x - 1))}$$

If compliance between two consecutive visits cannot be determined (e.g., if a participant does not return medication at the scheduled time), then compliance will be averaged across the periods that are affected.

For between-visit compliance, periods from unscheduled visits are assigned to nearest scheduled between visit periods.

The compliance will be summarized descriptively by treatment group and overall. In addition, compliance will be categorized into three groups (< 80%, 80-120%, > 120%) and summarized by treatment group and overall.

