6.1 Study Intervention(s) Administered

Table 6-1: Study interventions administered

Group Name	BAY 1817080	BAY 1817080 Placebo	Elagolix
Intervention Name	BAY 1817080	placebo for BAY 1817080	elagolix
Туре	drug	placebo	drug
Dose	tablet	tablet	tablet
Formulation			
Unit Dose	25 mg and 100 mg	N/A	150 mg
Strength(s)			
Dosage Level(s)	25 mg, 75 mg and 150	N/A	150 mg QD
	mg BID		
Route of	oral	oral	oral
Administration			
Use	experimental	placebo	active comparator
Packaging and Labeling	Study Intervention will be provided in blisters. Study Intervention will be labeled as required per country requirement	Study Intervention will be provided in blisters. Study Intervention will be labeled as required per country requirement	Study Intervention will be provided in blisters. Study Intervention will be labeled as required per country requirement
[Current/Former Name(s) or Alias(es)]	N/A	N/A	Orilissa ®

- Participants will take study intervention:
 - BAY 1817080 or matching placebo twice daily (morning and evening doses) at approximately the same time each day 12 hours apart, OR
 - o Elagolix once daily at approximately the same time each day 24 hours apart.
 - o To the effect that they will receive (according to assigned treatment groups):
 - Treatment group 1: 2 tablets of 25 mg BAY 1817080, 1 tablet of 100mg BAY 1817080 and one tablet of 25 mg placebo to BAY 1817080
 - Treatment group 2: 3 tablets of 25 mg BAY 1817080 and one tablet of 100mg placebo to BAY 1817080

27 JAN 2022 Page: 42 of 99

- Treatment group 3: 1 tablet of 25mg BAY 1817080, 2 tablets of 25mg placebo to BAY 1817080 and one tablet of 100mg placebo to BAY 1817080
- Treatment group 4: 3 tablets of placebo for 25mg, and 1 tablet of placebo for 100mg placebo to BAY 1817080
- Treatment group 5: One tablet of elagolix 150mg

For Treatment groups 1-4 participants will receive Placebo for BAY 1817080 due to blinding reasons. Participants are recommended to take the tablets at approximately the same time each day with or without food.

- Participants from China and Japan will only be randomized to treatment groups 1 to 4.
- Study interventions are not to be broken, halved or crushed; they should be swallowed as a complete unit with water.
- Study intervention can be taken with food or without food. See Section 8.4 for detailed instructions regarding recording of the drug intake and the food intake before or after the drug intake in relation to blood sampling for PK.

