- assess efficacy of BAY 1817080 compared to placebo and elagolix 150mg in the treatment of EAPP during days without vaginal bleeding ('non-menstrual pelvic pain') at weeks 4 / 8 / and of intervention period
- further describe the patient population, efficacy profile of BAY 1817080 and change during the study period using the data collected by patient reported outcomes
- assess sustainability of treatment effect and recurrence of symptoms

[figure not shown]
- describe sleep and physical activity associated measurements collected with accelerometer

A table that lists all primary, secondary, and exploratory objectives with the corresponding endpoints can be found in section 3 of the CSP. Additional other objectives listed in the CSP refer to analyses that are outside the scope of this SAP, and thus are not described in this document.

3. Study Design

This study is a placebo and active-controlled, double-blind, but open-label for the active comparator, randomized, parallel-group multi-center study. The study will be conducted in multiple clinical centers across Europe, North America, China, and Japan who take care of women with symptomatic endometriosis. An overview of the study design is shown in Figure 1.

Figure 1: Schema

*Follow-up 2 will be performed additionally in the 1st 50 % of randomized participants only. Follow-up 2 will extend to 90±3 days after the last administration of study intervention

Five treatment groups will be investigated: 25 mg, 75 mg, and 150 mg BAY 1817080 (referred to as low, mid, and high dosage group), placebo group and Elagolix group. The subjects will take 4 tablets twice daily (thus, 8 per day), containing BAY 1817080 or matching placebo, or 1 capsule once daily, containing 150 mg Elagolix. The treatment duration will be 12 weeks (84+3 days).

To achieve 50 evaluable participants for the primary analysis in each treatment arm, 840 participants were planned to be screened to start study intervention in about 420 randomized participants. Among them approximately 28 subjects from Japan with clinically confirmed instead of visually confirmed endometriosis and approximately 28 participants from China were planned to be randomised. None of the two groups will be included in the primary analysis.

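### SAP 6.4.2 omits the inclusive +1 day from the BAY 1817080 dose formulas and the BAY/placebo compliance formula, so both read slightly high and cannot be computed for one-day users

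*SAP*

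**What the plan says.** SAP 6.4.2 counts days in two ways.

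- **Inclusive count.** Treatment duration is "last dose date – first dose date + 1- number of days treatment was interrupted due to COVID-19 pandemic-related reasons". Both elagolix formulas, for average daily dose and for compliance (the latter introduced by "In addition, overall Compliance for the Elagolix arm will be calculated as"), have a denominator ending in "first tablets dispensed date}) + 1".
- **Plain date difference.** The average-daily-dose formulas for the 25, 75 and 150 mg arms, and the overall-compliance formula introduced by "Overall Compliance will be calculated as", divide by the earlier of last return and last intake, minus the first dispensing date. Nothing is added. In the compliance formula this difference is multiplied by 14.

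The dose part has limited scope: "the average daily dose for overall study is calculated for subjects on active treatment". It therefore concerns the three BAY 1817080 arms and not placebo, whereas the compliance formula serves BAY 1817080 and placebo alike. The between-visit compliance formula also uses a plain date difference. Compliance is then tabulated as below 80%, 80–120% and above 120%. The SAP gives no reason for the two conventions and no rule for a zero denominator.

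**The concern.** The tablets in the numerator come from every calendar day from first to last intake. The protocol's Schedule of Activities has drug dispensed at Visit 2 (Day 1) and the first dose taken at the site at that visit. Protocol 8.4 has study drug given on site at Visit 5 after the pre-dose sample. Both end days therefore contribute tablets, yet the BAY/placebo denominator leaves one of those days out.

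Three things follow:

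- The same adherence is scored differently in the blinded arms and in the elagolix arm of one table.
- The average daily dose of BAY 1817080 can read above the assigned dose purely through day counting, in a programme halted for liver safety.
- A participant whose first and last intake fall on the same date has no computable value, although SAP 5.1 places anyone who took at least one tablet in the safety set.

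The immediate treatment stop in protocol Amendment 2 makes short exposures more likely, and the distortion is largest there.

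**Working it through.** **Inputs**

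- Tablets per day: "The subjects will take 4 tablets twice daily (thus, 8 per day" (SAP 3).
- Tablet mix per dose: three of the 25 mg type and one of the 100 mg type. Protocol 6.1 gives the placebo arm as "3 tablets of placebo for 25mg, and 1 tablet of placebo for 100mg placebo to BAY 1817080", and the BAY arms have the same structure.
- First dose on the dispensing day: protocol Schedule of Activities. Visit 5 dose on site: protocol 8.4.
- Planned duration 84 (+3) days; compliance bands as above.

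**Step 1: reproduce the plan's own constants.** With a 25 mg tablet weighted 1 and a 100 mg tablet weighted 4, units per day are 2 × (3 × 1 + 1 × 4) = 14, which matches the SAP. On one full dosing day the dose numerators give:

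- 25 mg arm: 25 × (1/3 × 6) = 50 mg
- 75 mg arm: 25 × 6 = 150 mg
- 150 mg arm: 25 × (2/3 × 6) + 100 × 2 = 300 mg

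The tablet weights are right, so only the day count is in question.

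**Step 2: compliance under full adherence.** Let D be the inclusive number of treatment days. Each dose is worth 7 units.

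- Two doses on every day: 2D doses. SAP formula = 7 × 2D / [14(D − 1)] = D/(D − 1). With a plain +1 it is 100%.
- Two doses on Day 1 and one on the last day: 2D − 1 doses. SAP formula = (2D − 1)/[2(D − 1)]. With a plain +1 it is (2D − 1)/(2D).

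| D | SAP, two last-day doses | SAP, one last-day dose | Plain +1, two last-day doses | Plain +1, one last-day dose |
|---|---|---|---|---|
| 84 | 101.2% | 100.6% | 100% | 99.4% |
| 28 | 103.7% | 101.9% | 100% | 98.2% |
| 14 | 107.7% | 103.8% | 100% | 96.4% |
| 6 | 120.0% | 110.0% | 100% | 91.7% |
| 5 | 125.0% | 112.5% | 100% | 90.0% |
| 4 | 133.3% | 116.7% | 100% | 87.5% |
| 3 | 150.0% | 125.0% | 100% | 83.3% |
| 2 | 200.0% | 150.0% | 100% | 75.0% |

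At D = 1 the SAP denominator is 14 × 0 = 0. A plain +1 gives 100% if both doses were taken that day and 50% if only the on-site dose was taken. Elagolix is taken once daily, so D days hold D doses and its formula gives D/D = 100% at every D, including D = 1.

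**Step 3: average daily dose, 150 mg BID arm, D = 84.**

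- SAP formula: 300 × 84/83 = 303.6 mg (two last-day doses) or 150 × 167/83 = 301.8 mg (one).
- Inclusive days: 300 × 84/84 = 300.0 mg or 150 × 167/84 = 298.2 mg.

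**Step 4: the 80% boundary, relative to an inclusive-day count.** A true 80 × 83/84 = 79.05% at 84 days reads as 80%. At 14 days, 80 × 13/14 = 74.3% reads as 80%.

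**Step 5: between-visit compliance.** Adjoining intervals share a visit date, so a plain difference counts each day once. Only the last interval, when it ends at last intake, has the same end-day problem.

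**The case against.** The best defence is that different day counts can suit different regimens. For once-daily elagolix, +1 is exact. For a twice-daily product, a plain date difference is exact if the first and last dates each carry one dose: (2D − 2)/[2(D − 1)] = 100%. The right denominator therefore lies between D − 1 and D, and the difference between arms does not by itself prove an error. SAP 7 also records that the overall and between-visit definitions were aligned at compound level, so the form may be deliberate.

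Part of this stands. At Visit 5 a scheduled completer takes the dose given on site and returns her study drug, so one last-day dose is the pattern to expect. The overstatement is then half a day, not a full day, and the two-dose column above is the upper end. That column is still possible for someone told to stop after taking both doses.

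The defence does not clear the formula. Protocol 8.4 times the Visit 2 post-dose samples from the first dose of that day, which implies a second dose on Day 1, so the exact-match pattern is not the planned one. The zero denominator at D = 1 arises under every pattern.

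A reader might also infer that adherent early stoppers generally land above 120%. The documents do not support that. It needs an exposure of 2–3 days with one last-day dose, or 2–5 days with two. A fully adherent participant stopped at week 4 or 8 stays within 80–120% under either day count. The documents give no number of very short exposures.

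**Conclusion.** The point holds as a small day-count inconsistency with one case that cannot be computed. BAY/placebo compliance is overstated by half a day to one day: 0.6 to 1.2 percentage points at 84 days and 3.8 to 7.7 at 14 days, for full adherence. The 150 mg BID mean daily dose reads about 302 to 304 mg at 84 days, against 298.2 to 300 mg on inclusive days. These figures assume two doses on Day 1, one or two on the last day, and last intake no later than the last return.

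The reach is limited to descriptive exposure and compliance tables. A reader might infer that the primary result is biased. SAP 6.2.1 handles non-compliance by treatment policy and keeps data from non-compliant periods as observed, so the documents give no such route. Whether compliance can lead to exclusion from the per-protocol sets is left to a separate specification that is not available here, so nothing is claimed on that.

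**What to change.** In SAP 6.4.2:

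- **Average daily dose, 25, 75 and 150 mg arms:** add +1 to the denominators, matching the SAP's own duration and elagolix convention.
- **Overall compliance, BAY/placebo:** set the denominator to 7 × expected doses, where expected doses are 2 per inclusive day, less any dose not due on the first or last day. This returns 100% for full adherence under every end-day pattern and defines the one-day case.
- **Between-visit compliance:** apply the same count to the last interval when it ends at last intake, and leave the other intervals as they are.
- State in the text how doses due on the end days are identified, including for participants stopped at the hold.

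The cost is a small program change and the need to establish which doses were due on the end days. A plain +1 in the compliance formula is simpler, but it is not free of error. When only the morning dose is due on the last day it understates by half a day: 99.4% at 84 days, and 75% at D = 2, which would put a fully adherent participant below 80%.
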